### Ancillary Study at NIH:

During consent for this study, participants will be informed an optional study that will be performed at the NIH to measure an additional outcome of total energy expenditure using a whole room indirect calorimetry (WRIC). WRIC allows detailed assessment of energy and nutrient balance. Measurements are conducted at stable interior (room) temperature, humidity and barometric pressure, which are continuously measured. The NIH will have its own written consent and IRB procedures performed on its Bethesda campus. For participants that choose to participate in the NIH study, their WRIC data will be uploaded into a REDCAP database and transferred to our encrypted database for integration with other study outcomes.

### Data Analysis and Anticipated Outcomes:

The primary outcomes are nocturnal glucose and FFA levels. The main independent variable is experimental condition: [CPAP], [OSA+placebo], or [OSA+propranolol]. Since glucose and FFA are measured multiple times per subject per night, we will perform mixed linear model analysis using condition as a fixed factor and subject ID as a random factor. We will also examine whether there are independent or interacting effects of time, or time x condition on trajectories of FFA and glucose. We hypothesize that OSA increases glucose and FFA levels during [OSA + placebo] nights, compared to [CPAP], or [OSA + placebo] nights. We further hypothesize that propranolol will suppress nocturnal FFA and glucose to levels similar to that of CPAP. Sleep physiology that is measured on a continuous basis will be condensed into 30 minute bins to create a parallel data structure with metabolic parameters. We will then examine whether sleep physiology (e.g. AHI, arousals, heart rate) is dynamically associated with glucose or FFA, and whether urine catecholamine levels are associated with increases in FFA or glucose. For variables measured once (RHI, morning lipid profile) or averaged together (e.g. nocturnal glucose level) we will perform one-way ANOVA for comparisons. We will also compare sleep physiology between the 3 nights, examining variables such as apnea hypopnea index, metrics of hypoxia, and sleep architecture/duration. A questionnaire will be administered each morning to assess subjective sleep quality from the night prior, and to screen for any symptoms related to study medication. These responses will be used to determine how symptomatic a subject's OSA is, whether subjective sleep quality correlates with extent of metabolic change, and whether any side effects of beta blockade were perceived.

Regarding tracer data, we predict that  $R_a$  FFA and  $R_a$  glycerol will exhibit a ~3:1 ratio reflecting typical patterns of lipolysis without significant intra-cellular recycling. Based on studies of normal sleep [39, 40], we predict that on CPAP, sleep reduces lipolysis and FAO compared to wakefulness. During CPAP withdrawal, sleep will increase lipolysis (or at least mitigate sleep-induced suppression) compared to wakefulness. We hypothesize that FAO will be reduced or unchanged by OSA. This pattern of increased lipolysis without increased FAO may lead to

ectopic lipid deposition and extracellular TG cycling (see figure).

**b. Study duration and number of study visits required of research participants.**

Each subject will undergo 3 sleep studies spaced one week apart. Including the baseline consent/screening/randomization visit, there are a total of 4 study visits. Since visits are 1 week apart, the duration of involvement will be ~3 weeks. In the event that participants are not available to make visits exactly 1 week apart, we will allow visits to be spaced apart by  $\geq$  4 days and  $\leq$  3 weeks. Therefore, the minimum duration in the study is about 2 weeks, and the maximum time is 6 weeks.

If participants agree to being contacted for the ancillary calorimetry experiments, the time frame will be at least 1 week following completion of the PROSAT protocol. Participants will undergo 2 visits to the NIH (1 week apart) and under conditions of CPAP or NDS (CPAP withdrawal).

**c. Blinding, including justification for blinding or not blinding the trial, if applicable.**

The subject and investigator will be blinded to whether they receive placebo or propranolol. This will control for the potential placebo effect of taking any medication before sleep. The investigator will unblind the drug assignment after the first 6 completed participants, so that adjustments to propranolol timing or dosage can be performed depending upon hemodynamic and metabolic effects. At that point, if the average OSA-induced FFA level is not reduced by at least 10%, the dosage of Inderal LA will be increased from 80 to 120 mg. The dosage will be reduced if there is any evidence of excessive bradycardia ( $>15\%$  reduction in heart rate) or hypotension (systolic BP $<90$ ). In addition, if the FFA nadir does not occur during the main sleep period, the timing of propranolol administration will be advanced or delayed as necessary. These adjustments will be made in collaboration with the research pharmacy. Regardless of whether the PI is blinded or unblinded, all data collection (sleep study, EndoPAT etc) will be performed in a blinded manner. For CPAP withdrawal nights, NDS will be used as a CPAP placebo. This will control for unintended effects of stopping CPAP such as anxiety before sleep.

**d. Justification of why participants will not receive routine care or will have current therapy stopped.**

CPAP will be discontinued for a short period of time to elicit OSA. CPAP withdrawal induces the same sympathomimetic, neurocognitive, and vascular consequences of OSA as in treatment naïve subjects [33-36] indicating that findings from CPAP withdrawal studies are relevant to the untreated OSA population. Outcomes of this study – acute changes in lipid and glucose metabolism - are unlikely to irreversibly change with antecedent CPAP use. Another advantage is that retention in the study will be higher than enrolling treatment naïve patients, many of whom will be unwilling or unable to defer, to start, or to maintain CPAP therapy. Thus, a transient change in physiology in a small group of patients is being elicited with CPAP withdrawal to reveal mechanisms that may prevent refractory pathology in millions of others with OSA. There is no other deviation from routine care in this study.

**e. Justification for inclusion of a placebo or non-treatment group.**

In terms of NDS as a CPAP placebo during withdrawal nights, we wish to minimize confounding that might be introduced by other factors such as anxiety about stopping CPAP. Participants will be told that NDS are not as effective as CPAP for treatment of OSA. The written consent will state that NDS may be effective for nasal congestion but that long-term data have not shown an effect on OSA severity. In terms of the drug intervention, participants will be informed that we are studying the metabolic and vascular consequences of OSA and whether a medication taken before sleep can prevent these consequences. Propranolol is not being utilized as a therapeutic agent but as a mechanistic tool. Placebo is used to control for subconscious effects of taking a medication before sleep.

**Definition of treatment failure or participant removal criteria.**

Participants will be removed from the study if they do not meet eligibility criteria. Otherwise, this study is expected to induce OSA and its consequences, and the drug is being used as a tool to test mechanisms rather than treat a specific disorder. Patients may be removed from the study if they elect to withdrawal at any time.

**f. Description of what happens to participants receiving therapy when study ends or if a participant's participation in the study ends prematurely.**

Propranolol is given only one time per participant and is not considered therapy, but a mechanistic intervention. After each study visit, CPAP is resumed. Sleep study results will be discussed with the patient upon completion of the study. When clinically appropriate, referral for treatment will be provided. Patients may request results of their sleep study before completion of the study.

## **5. Inclusion/Exclusion Criteria**

This study is similar to "MIIC: Metabolic Impact of Intermittent CPAP" (NA\_00086830) in terms of CPAP withdrawal procedures. Thus, inclusion/exclusion criteria are similar but are expanded to exclude patients with contraindications to taking beta blockers. In addition, we are attempting to enrich the cohort with participants who exhibit high FFA or glucose levels during CPAP withdrawal. Participants who completed their involvement in MIIC, who have resumed CPAP for at least 1 month, may enroll in this study. They must have exhibited a FFA or glucose elevation of  $\geq 10\%$  during their CPAP withdrawal study.

**Inclusion Criteria:**

1. Men and women of all races  $\geq 20$  and  $\leq 70$  years old
2. History of OSA (AHI $>20$ ,  $>50\%$  events obstructive)
3. Accustomed to CPAP use, and willing to discontinue CPAP temporarily for the study and switch to NDS
4. If the participant has already completed "Metabolic Impact of Intermittent CPAP" (NA\_00086830, they must have exhibited a  $>10\%$  increase in nocturnal FFA or glucose during CPAP.

**Exclusion Criteria:**

1. Cardiovascular risks
  - a. Decompensated congestive heart failure
  - b. Atrial fibrillation, sick sinus syndrome, 2nd or 3rd degree heart block, pacemaker implantation, Wolff-Parkinson-White Syndrome (if not known, will check on a screening EKG)
  - c. Uncontrolled hypertension  $> 170/110$
  - d. History of postural hypotension.
  - e. Resting systolic pressure  $<90$  or heart rate  $< 50$  on screening visit
2. Drug interactions – currently taking any of the following drugs Subjects on these medications are excluded from participation and will not have the drug in question discontinued for the purposes of participation in the study.
  - a. Calcium channel blockers that reduce heart rate (diltiazem, verapamil, fendiline, gallopamil)
  - b. Sympatholytic drugs: any other beta blocker; clonidine, terazosin or doxazosin; reserpine
  - c. Anti-arrhythmic drugs: (e.g. amiodarone, sotalol, digoxin, quinidine, lidocaine, propafenone)
  - d. Coumadin (propranolol may prolong INR)
  - e. Drugs that Inhibit CYP2D6, CYP1A2, or CYP2C19: amiodarone, ciprofloxacin, cimetidine, delavudin, fluconazole, fluoxetine, fluvoxamine, imipramine, isoniazid, paroxetine, quinidine, ritonavir, rizatriptan, tenioposide, theophylline, tolbutamide, zileuton, zolmitriptan
  - f. Drugs that increase hepatic metabolism of propranolol: rifampin, ethanol, phenytoin, and phenobarbital
  - g. Neuroleptics/anxiolytics: (thioridazine, chlorpromazine – may increase propranolol level), haloperidol, valium
  - h. Illicit drugs such as cocaine or amphetamines.

3. Other medical conditions
  - a. Sleep disorder other than OSA, including: restless leg syndrome, parasomnia, or narcolepsy.
  - b. Shift work or circadian rhythm disorder that is expected to prevent good sleep as scheduled in the protocol
  - c. Insulin-dependent diabetes mellitus
  - d. Myasthenia gravis
  - e. Pheochromocytoma
  - f. Uncontrolled bronchospastic lung disease such as COPD, mild persistent or worse asthma, as well as those requiring maintenance therapy.
  - g. Current smoking
  - h. Chronic renal or liver failure
  - i. Known pregnancy, by urine testing in women of child-bearing age; nursing mothers
  - j. Known hypersensitivity to any beta blocker
  - k. Hemoglobin < 10 g/dL on point of care screening
4. Patients with a history of falling asleep while driving, involved in a near-miss accident while driving, and those in high-risk occupations such as commercial drivers or pilots.

## 6. Drugs/ Substances/ Devices

- a. The rationale for choosing the drug and dose or for choosing the device to be used.

FFA and glucose elevations occur during the night in OSA patients (fig 1), and these elevations may be responsible for adverse cardio-metabolic consequences of OSA. The SNS is well known to mediate adipose tissue lipolysis as well as “stress hyperglycemia”. Thus, we may be able to mitigate these nocturnal metabolic changes with beta adrenergic blockade. We selected propranolol because it (1) is a non-selective beta antagonist that broadly inhibits norepinephrine-simulated lipolysis; (2) is lipophilic and crosses the blood-brain barrier, which may be desirable in mitigating OSA-related distress; (3) is well tolerated in non-hypertensive subjects [27]; (4) is effective in preventing hyperglycemia and/or lipolysis in other acute stresses including burn trauma [21], surgery [28], high altitude hypoxia [29] and animal models of autonomic stress [30] [31]; (5) and is mechanistically revealing, as it does not block alpha adrenergic receptors which are less likely to be involved in the stress hyperglycemic effect in humans [28].

Propranolol is rapidly metabolized with a plasma elimination half-life of 2 to 4 hours, requiring up to 4 doses daily for management of hypertension or angina. In our study, patients will require beta blockade for > 12 hours, which is why long acting propranolol has been selected. The areas under the propranolol plasma concentration-time curve (AUCs) for sustained release propranolol are lower than for comparable divided daily doses of propranolol [41] [42].

In this study, we will administer a single dose of long-acting (or “sustained release”) propranolol (Inderal® LA) 80 mg at 7:00 PM. This is the standard clinical starting dose for hypertension, and less than the nighttime dose of propranolol LA 120 mg used in a study of patients with bruxism[43]. The drug is coated with a semipermeable membrane to allow gradual absorption over a 12 hour period and a therapeutic window lasting ~24 hr. In a pharmacokinetic study, 160 mg of sustained release propranolol demonstrated gradual increase in plasma concentration to a peak ~6 hours after administration, then a gradual decline. By comparison, propranolol XL (Innopran XL) has a later onset of absorption, and a higher plasma peak and AUC than Inderal LA [44] which make it less desirable for this study. Propranolol LA 80 mg is less than the equivalent dosing of propranolol 40 T.I.D, the starting clinical dose for a variety of indications. For example, propranolol was used in the Beta Blocker Heart Attack Trial (BHAT, n=3,837), which administered 40 mg T.I.D, and later titrated up to 80 mg T.I.D [45]. In migraine headache, typical dosing is up to 160 mg propranolol daily in divided doses [46]. Propranolol LA at 160 mg daily is the target clinical dose in studies of angina pectoris, hypertension, and hyperthyroidism[42].

After interim analysis of the first 6 participants, we may adjust the dose and/or timing of propranolol based on its safety and efficacy, if necessary. For safety, the criterion is that on the propranolol night, the median heart rate during sleep should decrease by no more than 15% of basal heart rate as measured during the

placebo night. In addition, systolic blood pressure on the propranolol night should remain  $\geq 90$  mmHg. For efficacy, the decrease in overnight FFA levels by propranolol needs to be at least 10% as compared to the placebo night.

During CPAP withdrawal nights (both at home and in the lab) we will use NDS as a CPAP placebo. NDS may improve snoring but have no treatment value for OSA [38]. By including NDS as a placebo, we will avoid potential confounding such as anxiety caused by stopping CPAP.

Stable isotope (non-radioactive) tracers are being used in this project to quantify rates of adipose tissue lipolysis (infusions of [ $U-^{13}C_3$ ]glycerol and [ $U-^{13}C_{16}$ ]palmitate) and rates of fatty acid oxidation (FAO, ingestion of [ $^2H_{31}$ ]palmitate and  $H_2^{18}O$ ). These tracers have been used safely in several metabolic research studies [47-50]. The breakdown of stored triglycerides (lipolysis) results in the release of fatty acids and glycerol from fat cells. Thus, the rates of release of fatty acids and glycerol into the bloodstream reflect rate of lipolysis, which are usually measured by the constant-infusion-isotope-dilution technique [51]. In this approach, labelled fatty acid and glycerol are infused intravenously in tracer amounts at a constant rate. The  $R_a$  of endogenous unlabeled fatty acids and glycerol into the bloodstream can be determined by calculating the dilution of the infused isotope [51]. Labelled palmitate is usually used as the tracer since it is the typical of other fatty acids and reflects whole-body free fatty acid kinetics [51]. The palmitate tracer will be bound to albumin for infusion, since it is not soluble in water [51]. We chose [ $U-^{13}C_{16}$ ]palmitate and [ $U-^{13}C_3$ ]glycerol for infusion as they are uniformly carbon-labeled stable isotopes with high detection sensitivity which require lower dose and infusion rate as compared to single carbon labeled tracers [52]. The infusion is given at a "tracer" dose detectable only by gas chromatography/mass spectroscopy (GC/MS). The dose and infusion rate of the isotopes will depend upon the subject's body weight. Specifically, we will administer a constant infusion of [ $U-^{13}C_3$ ]glycerol  $0.1 \mu\text{mol} \cdot \text{kg}^{-1} \cdot \text{min}^{-1}$  ( $\times 12$  hours) =  $72 \mu\text{mol}/\text{kg}$  of total per night (approximately  $8.64 \text{ mmol} = 2.68\text{g}$  for a  $120\text{kg}$  person, Sigma-Aldrich 660701), and [ $U-^{13}C_{16}$ ]palmitate will be infused  $0.04 \mu\text{mol} \cdot \text{kg}^{-1} \cdot \text{min}^{-1}$  for 1-hour intervals ( $\times 4$ ) =  $9.6 \mu\text{mol}/\text{kg}$  of total per night (approximately  $1.152 \text{ mmol} = 0.36\text{g}$  for a  $120\text{kg}$  person, Sigma-Aldrich 687871).

Stable isotopes [ $^2H_{31}$ ]palmitate and  $H_2^{18}O$  will be used to follow the fate of ingested fat (palmitate), and to quantify the plasma water pool size to permit calculation of tracer oxidation rate. This is a validated technique to quantify FAO by providing an oral liquid dose of [ $^2H_{31}$ ] palmitate taken with dinner [53]. We will administer [ $^2H_{31}$ ] palmitate orally with dinner in a liquid emulsion (such as an Ensure® shake) at a dose of  $15 \text{ mg/kg}$  body weight (approximately  $1.7 \text{ g}$  of fat for a  $120 \text{ kg}$  person, Cambridge Isotope Laboratories DLM-215-MPT). In addition, we will administer a stable isotope of water, [ $H_2^{18}O$ ] 10% orally at a dose of  $0.4 \text{ g/kg}$  body weight (about  $48 \text{ mL}$  for a  $120\text{-kg}$  person, Cambridge Isotope Laboratories OLM-240-10-0). When [ $^2H_{31}$ ]palmitate is oxidized, the  $^2H$  is released into the plasma  $^2H_2O$  and is quantified by mass spectroscopy.

**b. Justification and safety information if FDA approved drugs will be administered for non-FDA approved indications or if doses or routes of administration or participant populations are changed.**

We will be administering unmodified, marketed product via the typical oral route at a standard clinical dose. This proposal was presented the FDA and qualified as exempt from IND application (see separate documentation). Propranolol is FDA approved for indications including hypertension, migraine, supraventricular tachycardia, and essential tremor and lawfully marketed in the United States. This research is not intended to support any change in the advertising or labeling of the drug. A conventional starting dose of drug is being administered, and the drug will be administered one time during the study. The investigator will not represent the drug in any promotional context, distribute, test-market, or charge for the drug.

Propranolol is a non-selective (beta-1 and beta-2 receptor), non-vasodilating beta adrenergic receptor antagonist. It has been used for decades for hypertension and angina as well as "off label" for other

indications such as anxiety. It has been used in research settings to inhibit SNS responses to a variety of environmental stressors. Beta blockers such as atenolol [24] and nebivolol [25] have been safely studied in OSA-related hypertension. Clinical and chronic beta blocker use does not aggravate apnea-induced heart rate decelerations [26]. In an animal study of experimental OSA, propranolol blunted arousal-induced tachycardia and hypertension without exacerbating bradycardia during apneas [54]. Propranolol LA 120 mg has been given as a single dose before sleep and reduces heart rate without lowering blood pressure [43]. Propranolol has been used since the 1970's for anxiety in non-hypertensive patients [27]. In a pharmacokinetic study of propranolol in normotensive men, a single dose of Inderal LA 160 mg caused a mean peak reduction of systolic blood pressure of 11.6 mmHg and 8 BPM reduction in heart rate[44].

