and CPAP airflow. Therefore, we use a validated technique to quantify differences in FAO between studies by providing an oral liquid dose of 15 mg/kg body mass of [H31]palmitate taken with dinner. The isotope is dissolved in a warm (60 °C) liquid shake (such as Ensure®). The isotope is non-radioactive and synthetic (Cambridge Isotope Laboratories DLM-215-MPT). FAO will be quantified thereafter by hourly assessment of deuterium incorporation into plasma H2O using anisotope ratio MS (IR/MS). Subjects will also ingest 0.4 g/kg body mass of H2O (10% enriched; CIL OLM-240-10-0, Andover MA) to calculate total body water (TBW) by isotope dilution. The FAO rate will be determined by excess plasma H times TBW, while percent recovery of deuterium will be determined by dividing by dose of H administered. All tracers in this protocol are tested for microbiological contamination, and are exempt from FDA IND status (see email correspondence with FDA # PIND 132066). The isotopes of H O and [H31]palmitate are stored in the PI's laboratory. Their required amount is prepared for each participant and brought to the CRU. The [H31]palmitate is dissolved in an Ensure shake and heated in the kitchen by nursing staff or dietitian in CRU.

*Blood sampling and morning urine sample collection.* The first blood sample is taken at 5:30 PM, just before dinner and serves as a pre-medication, pre-isotope baseline. Subsequent samples are drawn hourly while the subject is awake. At 10:30 PM, when the sleep study starts, blood is sampled more frequently, at 30 minute intervals in order to capture dynamic changes in metabolism during sleep. Additional samples will be drawn towards the end of each palmitate infusion period, to ensure a plateau of isotope enrichment. Each blood sample will be 4 cc in volume and placed into lavender top tubes (EDTA) for centrifugation to obtain plasma. Cells are removed from plasma by centrifugation for 10 minutes at 1500 x using a refrigerated centrifuge. Following centrifugation, plasma will be transferred to cryovials for storage. In patients that have signed the optional consent for isolation of genetic material, we will collect an additional 16 cc (4 tubes) at 6:30 AM upon awakening since this volume is required for isolation of peripheral mononuclear cells. The final sample is obtained at 9:00 AM. .

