**7. Study Statistics**

- a. Primary outcome variable: Nocturnal FFA and glucose profile
- b. Secondary outcome variables: Morning EndoPAT, lipid panel. Sleep study parameters (e.g. total sleep time, latency, wake after sleep onset, sleep stages, AHI, oximetry, heart rate). Lipid flux data (rate of lipolysis and FFA turnover using stable isotope data; rate of fatty acid oxidation), DNA methylation profile.
- c. Statistical plan including sample size justification and interim data analysis.

**Comparisons between CPAP, [NDS + propranolol], and [NDS + Placebo]:** Primary outcome is comparison of metabolism and blood pressure for [NDS + propranolol] versus [NDS + placebo]. For metabolic parameters that are repeatedly measured during sleep (e.g. FFA, glucose) we will use mixed linear model analysis with experimental group as a fixed factor and subject ID as a random factor. Sleep physiology that is measured on a continuous basis (e.g. heart rate, AHI, SpO2) will be condensed into 30 minute bins to create a parallel data structure with metabolic parameters. We will then examine whether these sleep physiological metrics are dynamically associated with glucose/FFA level. For those parameters that are measured once per visit (e.g. RHI, lipid panel), we will compare using paired T-tests for within-subject comparisons between nights. A secondary outcome is whether CPAP and [NDS + propranolol] are similar, and this will be performed using a similar pairwise comparison. In addition, one way ANOVA will be used to ascertain whether there is a detectable difference across all three groups. Multiple regression will be used to examine associations between FFA, glucose, CPAP status, and drug adjusting for potential confounders such as diabetes, BMI, body fat (DEXA) and age. As an exploratory analysis, Pearson correlation matrices will be used to probe the interrelatedness of glucose, FFA, insulin, lipids, and sleep outcomes, followed by targeted multivariable regression. We plan an analysis of each subject's pulse rate and blood pressure after their PSG to determine whether beta blocker dosage or timing requires adjustment, which will expedite the ability to tailor the therapy if necessary.

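### The fatty acid oxidation outcome measures oxidation of palmitate eaten at dinner, so it cannot show that lipolysis rises without a matching rise in oxidation of the fatty acids released

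*Protocol*

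**What the plan says.** **Lipolysis.** Protocol section 4 (Stable isotope ingestion and infusions) infuses [13C3]glycerol and [13C16]palmitate and derives rates of appearance (Ra) from their plasma enrichment. These describe endogenous fatty acids.

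**Oxidation.** The same section uses a different tracer by a different route, deuterated palmitate swallowed at dinner: "we use a validated technique to quantify differences in FAO between studies by providing an oral liquid dose of 15 mg/kg body mass". The calculation is given as "The FAO rate will be determined by excess plasma 2 H times TBW" (total body water), and "percent recovery of deuterium will be determined by dividing by dose of" deuterium given. Section 6a states that the oral tracers "will be used to follow the fate of ingested fat (palmitate), and to quantify the plasma water pool size to permit calculation of tracer oxidation". The validation paper cited there (reference 53) is titled for dietary fat oxidation.

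**Label.** Section 7b lists the secondary outcome as "rate of lipolysis and FFA turnover using stable isotope data; rate of fatty acid oxidation", with no restriction to dietary fat.

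**Inference.** Data Analysis and Anticipated Outcomes predicts that lipolysis will rise, or fall less than usual in sleep, during CPAP withdrawal. It then says: "We hypothesize that FAO will be reduced or unchanged by OSA. This pattern of increased lipolysis without increased FAO may lead to". The consequences it goes on to name are fat deposited in ectopic sites and triglyceride cycling outside cells.

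**Standing.** Section 2 places lipolysis and oxidation among additional outcomes of interest. The SAP does not list oxidation; its metabolic secondary outcomes are FFA, glucose and insulin.

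**The concern.** The analysis section compares two quantities that concern different fatty acids. One is the release of stored fat into plasma; the other is the burning of a labelled fat eaten at about 5:30 PM. To say that released fatty acids are not being oxidised, one must measure the oxidation of those fatty acids. The oral tracer does not follow them, and the stated formula contains nothing that links it to them.

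The hypothesis is that FAO is reduced or unchanged. If the measure tends to read unchanged even when oxidation of released fatty acids has risen, a null reading will be taken as confirmation. A mechanistic conclusion about ectopic fat would then rest on a result that the assay would give either way.

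**Working it through.** The Protocol states no figure for this outcome, so there is none to reproduce. The check is tracer algebra with stated assumptions.

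**Inputs from the Protocol.** Oral tracer at dinner, about 5:30 PM; sleep study from 10:30 PM, 5 hours later; last blood sample at 9:00 AM. FAO is excess plasma deuterium × total body water, divided by dose for percent recovery.

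**Assumed, not in the documents.** m is the share of tracer oxidation that passes through the plasma FFA pool (0 to 1); the remaining share is unaffected by condition. The rise r in FFA appearance is set at 10%, 20% and 30% for illustration.

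**Formula.** Ratio of readings, OSA to CPAP = m × (oxidation ratio / Ra ratio) + (1 − m).

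**Step 1: oxidation rises in step with lipolysis.** Both ratios equal 1 + r, so the reading is m × 1 + (1 − m) = 1, a 0% change for every m and every r. With m = 1, dilution of the label by unlabelled fatty acids cancels the rise. With m = 0, the label never meets the released fatty acids and the measure is blind to them. A true rise of 20% reads as no change.

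**Step 2: oxidation is truly unchanged.** The reading is m/(1 + r) + (1 − m).

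| Rise in FFA appearance | m = 1 | m = 0.5 | m = 0 |
|---|---|---|---|
| 10% | 1/1.1 − 1 = −9.1% | −4.5% | 0% |
| 20% | 1/1.2 − 1 = −16.7% | −8.3% | 0% |
| 30% | 1/1.3 − 1 = −23.1% | −11.5% | 0% |

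The m = 1 column is an upper bound: full mixing, with the condition acting throughout.

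**Step 3: timing.** Assume that label is absorbed at 0.5 per hour. Of absorbed label, 20% is oxidised directly, 50% is stored and 30% enters plasma FFA; 40% of the plasma share is oxidised and the rest is stored. The condition acts only from 10:30 PM.

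- Without re-release of stored label, baseline recovery is 0.20 + 0.30 × 0.40 = 0.32.
- Label still unabsorbed at 10:30 PM is exp(−0.5 × 5) = 0.082.
- With a 20% rise in appearance and oxidation unchanged, recovery changes by 0.30 × 0.082 × 0.40 × (1/1.2 − 1) = −0.0016, which is −0.5% of 0.32.
- With stored label re-released at 0 to 20% per hour, unchanged oxidation reads between 0% and −0.5%, and a matched 20% rise in oxidation reads between 0% and about +5%.

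Dilution can therefore be negligible while most or all of a real rise is still missed.

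**The case against.** **The method is described as validated, and the choice is explained.** The Protocol says that breath collection and calorimetry would disrupt sleep, monitoring and CPAP. That justifies using the oral tracer. It does not make a dietary tracer a measure of endogenous oxidation. The stated purpose of comparing nights does not help either, because the nights are expected to differ in lipolysis.

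**Percent recovery of a known oral dose needs no precursor-enrichment term.** This stands. The formula is sound for dietary palmitate recovery; the fault lies in the label and the inference.

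**The ectopic-fat idea could survive a matched rise.** This also stands in part. If 40% of flux is oxidised (an assumption) and both flux and oxidation rise by 20%, non-oxidised flux rises from 0.60 to 0.60 × 1.2 = 0.72. The idea is not refuted, but the oral tracer does not establish it, and the clause saying that FAO does not rise would be wrong.

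**A stronger reading is tempting:** that extra lipolysis dilutes the tracer and biases the result towards the hypothesis by 9% to 23%, with the opposite bias on propranolol nights. The documents do not support it. They give no mixing fraction, and the tracer is eaten about 5 hours before the sleep study. Those percentages also belong to the case where oxidation is truly unchanged, in which the predicted pattern would be correct. No FAO hypothesis specific to propranolol is stated in the analysis section.

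**Conclusion.** The point holds as one of labelling and inference. The outcome is recovery of deuterium from dinner palmitate, and it cannot by itself show whether oxidation of endogenously released fatty acids rose. In the simple mixing calculation this does not depend on how much label mixes, provided that the directly oxidised share is unaffected by condition. Allowing re-release of stored label lets a little of the rise through: at most about 5% of a true 20% in the range tried.

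Dilution is a possible additional effect of unknown size, from near zero up to the full-mixing bounds in the table.

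Consequences are limited. Oxidation is a secondary or additional outcome in the Protocol and is absent from the SAP. Glucose and FFA levels, the SAP's heart rate outcome and the sample sizes are untouched.

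**What to change.** - In Data Analysis and Anticipated Outcomes and in section 7b, rename the outcome *dietary palmitate oxidation (percent of oral dose recovered)*.
- State that it cannot by itself show whether oxidation of endogenously released fatty acids rose. Drop or qualify the clause that FAO does not increase, and the ectopic-deposition inference drawn from it.
- If deuterated palmitate is measurable in plasma, its enrichment may be reported as an exploratory sensitivity check. It should not be used as a correction: scaling by it assumes that the oxidised label passed through plasma FFA, which the documents do not settle.
- The optional NIH calorimetry may be cited as context only. It gives total energy expenditure under CPAP or nasal dilator strips, at least a week after the main study, with no propranolol condition.

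The cost is wording, plus some assay work if the exploratory check is attempted. The price is a weaker mechanistic claim.
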